**STUDY PROTOCOL****Prospective Multicenter Study on Localization Accuracy and Clinical Utility of Automated Electric Source Imaging in Presurgical Evaluation( PROMAESIS)**

Brief Title: Clinical Utility of Automated Electric Source Imaging in Presurgical Evaluation (PROMAESIS)

Identifiers: NCT04218812; Unique Protocol ID: PROMAESIS

Date: August 8, 2018

*Goal:* to elucidate the accuracy and the clinical utility of automated electric source imaging (ESI) in presurgical evaluation.

*Primary outcome:* accuracy measures (sensitivity, specificity, positive and negative predictive values), overall accuracy (number of [TP and TN]/total patients).

*Secondary outcomes:* clinical utility (change in patient management decisions); inter-ESI-methods agreement (at sub-lobar level).

*Patients:* consecutive patients will be prospectively recruited from the EpiCare and E-epilepsy centers.

Inclusion criteria: patients with drug resistant focal epilepsy, admitted to EMU for presurgical evaluation, who are afterwards discussed at the multidisciplinary epilepsy surgery team meetings. Exclusion criterion: patients who did not have a seizure during the monitoring.

*Sample-size:* We expect a sensitivity of 80% and specificity of 60%. We expect that 50% of the investigated patients will be operated and 66% of them will become seizure-free. Calculating with an accuracy of estimate of 10%, we need 250 patients (Hess et al., Eur J Clin Microbiol Infect Dis (2012)).

*Recordings:* Although there will be variations from center-to-center concerning the EEG electrode array, we will attempt to achieve as much standardization as possible. Centers will use either caps or cup-electrodes (mounted individually).

- a) Caps: need to be of at least 64 electrodes (10-10 system), with even spatial distribution of the electrodes, and including the inferior electrode chain. The centers will specify how they place the cap relative to fiducials and other possible reference visible on the MRI. (For example; how far is the foremost midline electrode away from Nz and the most posterior electrode from Iz; how far is the most lateral inferior electrode away from the lateral eye corner).
- b) Cup-electrodes: we need at least the standardized electrode array of 40-electrodes, described in appendix-1.

Before starting the study, we will discuss with each center the electrode array they use, and we need to validate for the study each array that will be used in the study.

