- The minimum number of spikes in a cluster must be 20 spikes

The data of each cluster should contain:

- Number of spikes in each cluster
- Waveforms of 10 examples of spikes
- Averaged waveforms and voltage maps at peak and onset.  
All waveforms (+/-500 ms around the peak) will be provided filtered with a 1 Hz forward low filter and a high filter of 70 Hz both in longitudinal bipolar and common average montages.
- Source images for the two time-points (or epochs): onset and peak (in separate images). Images should be provided in transversal, sagittal and coronal views.
- BESA will also provide source waveforms for onset and peak (only one if not substantially different) and a current vector depicting the orientation of the spike source current.
- The analyzed ictal signal for each seizure-onset epoch in common average montage with marking of the cycles/epoch that has entered the analysis.
- The source images for each seizure-onset epoch.

For the interictal EDs we will use two different definitions of the “dominant” cluster:

- Quantitative definition: the cluster with the highest number of spikes
- Qualitative definition: each center will mark a spike as dominant, in the clinical context (thus not necessarily the most prevalent cluster).

*Reference standard (“gold standard”):* For determining accuracy (sensitivity, specificity, PPV and NPV) and overall accuracy ((TP+TN)/total) gold standard will be the resected site and the outcome one year after the operation:

- TP: source is in the same sub-lobar region as the resection, seizure-free outcome
- FP: source is in the same sub-lobar region as the resection, not seizure-free outcome
- TN: source outside the sub-lobar region that was resected, not seizure-free outcome
- FN: source outside the sub-lobar region that was resected, seizure-free outcome.

To enable an adequate comparison between methods, each method should create an ellipsoid around each center location (maximum of SLORETA, equivalent dipole location(s), seeded center of cortical CLARA / CLARA) indicating the likely error in localization due to electrode/registration inaccuracies and unknown conductivities. The ellipsoid has a larger axis in radial direction (2.5 cm) as compared to the tangential axes (1.8 cm), because of the large effect of the unknown conductivities on source depth.

For determining clinical utility, the percentage of patients in whom ESI changed decision on patient management (appendix-4) will be calculated.

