### **Appendix-3: The sub-lobar regions**

See the CRF for more details.

Side: left / right

Regions:

- Frontal
  - perisylvian-superior surface / operculum
  - lateral
  - mesial
  - polar
  - orbitofrontal
- temporal
  - mesial
  - polar
  - basal
  - lateral-anterior
  - lateral-posterior
  - perisylvian-inferior surface / operculum
- central
  - lateral convexity
  - mesial
  - central sulcus – anterior surface
  - central sulcus – posterior surface
  - perisylvian-superior surface / opercular
- parietal
  - lateral-convexity
  - mesial

- perisylvian-superior surface / opercular
- occipital
  - lateral
  - mesial
  - basal
- insula

**Appendix-4:** Logging the changes in decision on clinical management of the patients:

The multidisciplinary teams take decisions in two steps:

- I. Considering all data, except ESI
- II. Adding ESI to all other data.

At each step, the decisions are classified into one of the following categories:

1. Stop (operation not recommended)
2. Implantation of intracranial electrodes
3. Operation

In addition, the changes are classified into one of the following categories:

1. No change – but concordant with decision.
2. No change – but discordant with decision.
3. Change from stop to implantation.
4. Change from implantation to stop.
5. Change in implantation plan: implantation of additional sites (besides the ones planned in step-1).
6. Change from implantation to operation.
7. Change from operation to implantation.
8. Other (specify in free text).

If changes are not related to all analyses results, it will be noted, which method(s) triggered the change (SLORETA-interictal / ictal; ECD-interictal/ictal; CLARA interictal/ictal).

At one-year follow-up, the changes are categorized as useful or not useful. A change is defined useful as follows: (a) change from stop to ICR: the ICR localized the source; (b) change in implantation strategy: the electrode(s) implanted based on the EMSI identified the source; (c) change from implantation to operation: the patient became seizure-free.

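### The clinical-utility outcome counts every ESI-triggered change of decision, helpful or not, and the one-year useful/not-useful rating in Appendix-4 is not tied to it

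*Protocol*

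**What the plan says.** The opening summary of the protocol lists as a secondary outcome "clinical utility (change in patient management decisions". The end of the section on the reference standard gives the calculation: "the percentage of patients in whom ESI changed decision on patient management (appendix-4) will be calculated". Neither place requires the change to have been beneficial.

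Appendix-4 describes how changes are logged. "The multidisciplinary teams take decisions in two steps", first without ESI and then with it. The result is coded in eight categories. Codes 1 and 2 are for no change, and code 1 reads "No change – but concordant with decision". Codes 3 to 7 are specific changes, and code 8 is for anything else.

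Appendix-4 then adds an assessment of benefit: "At one-year follow-up, the changes are categorized as useful or not useful". It gives three criteria. The first is "a) change from stop to ICR: the ICR localized the source". The second concerns an altered implantation plan and asks whether contacts placed because of source imaging found the focus. The third is "c) change from implantation to operation: the patient became seizure-free".

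These correspond to codes 3, 5 and 6. No criterion is given for implantation to stop (code 4), operation to implantation (code 7) or other changes (code 8).

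**The concern.** Clinical utility is half of the study's stated goal, and the percentage changed is the only measure the protocol names for it. That percentage has no direction. A change that led to electrodes that found nothing, or to an operation that failed, adds as much as one that succeeded. An ESI that correctly confirms the team's plan adds nothing. The figure therefore measures how often ESI moves decisions, and a high value is compatible with no benefit.

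The information needed to separate the two is already planned under Appendix-4, but it is left outside the outcome. At stake is whether the study's statement on clinical utility can bear its label.

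**Working it through.** **Is there a figure to reproduce?** No. The protocol gives no expected rate, precision or sample size for clinical utility. The sample-size paragraph concerns sensitivity and specificity only.

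**Does any text link the rating to the outcome?** The reference-standard section cites Appendix-4, but the citation qualifies the decision that is changed, and the quantity calculated is the percentage changed. The paragraph on the four centers that do manual ESI points the same way. Their teams see the manual result only once utility of the automated analysis has been scored. There, utility is scored during the preoperative work-up, before a one-year rating can exist. No sentence in the protocol makes the rating part of this outcome or any other.

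**Can the percentage run against accuracy?** A simple model tests this. Its inputs are:

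- t, the probability that the team's localization before ESI is correct: assumed 0.66, varied from 0.4 to 0.8. The protocol gives no such figure.
- a, the probability that ESI is correct: varied from 0.4 to 0.9.
- K, the number of regions: 46 from Appendix-3, since 5 frontal + 6 temporal + 5 central + 3 parietal + 3 occipital + 1 insular = 23 per side, times 2. K = 2 serves as the simplest case.
- Errors independent, and every disagreement leads to a change: both assumed.

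The formulas are:

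- P(changed) = 1 − [t·a + (1 − t)(1 − a)/(K − 1)]
- P(wrong to right) = (1 − t)·a
- P(right to wrong) = t·(1 − a)

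Example with t = 0.66, a = 0.4, K = 46: P(changed) = 1 − [0.264 + 0.34 × 0.6/45] = 1 − 0.2685 = 73.1%; wrong to right = 0.34 × 0.4 = 13.6%; right to wrong = 0.66 × 0.6 = 39.6%.

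| ESI accuracy a (t = 0.66, K = 46) | Changed | Wrong to right | Right to wrong |
|---|---|---|---|
| 0.4 | 73.1% | 13.6% | 39.6% |
| 0.6 | 60.1% | 20.4% | 26.4% |
| 0.8 | 47.0% | 27.2% | 13.2% |
| 0.9 | 40.5% | 30.6% | 6.6% |

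The remainder of the changed column is one wrong region replaced by another. Correct confirmations, t·a, rise from 0.66 × 0.4 = 26.4% to 0.66 × 0.9 = 59.4% and earn no credit.

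**Sensitivity to the assumptions**, for a from 0.4 to 0.9:

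| K | t | Percentage changed |
|---|---|---|
| 46 | 0.4 | 83.2% to 63.9% |
| 46 | 0.5 | 79.3% to 54.9% |
| 46 | 0.8 | 67.7% to 28.0% |
| 2 | 0.8 | 56.0% to 26.0% |
| 2 | 0.66 | 53.2% to 37.2% |
| 2 | 0.5 | 50.0% throughout |
| 2 | 0.4 | 48.0% to 58.0% |

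The reversal is therefore not universal. Wrong-to-right changes rise with accuracy in every case, because (1 − t)·a does.

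**How far apart could the two percentages be?** Assume that 30% of the planned 250 patients have a change (0.30 × 250 = 75). The stated outcome is then 30%. The useful share is 0.30 × 0.3 = 9%, 0.30 × 0.5 = 15% or 0.30 × 0.7 = 21% if 30%, 50% or 70% of changes prove useful.

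**The case against.** The strongest reply is that the protocol does assess benefit. It does so in the very appendix that the outcome cites, and its criteria separate out electrodes that found nothing and operations that failed. On this view only a sentence on tabulation is missing, which a statistical analysis plan could supply. The first half stands: it would be wrong to say that the protocol ignores benefit. The second half does not. The protocol does not leave the calculation open; it states one, and that one omits the rating.

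A second reply is that accuracy is the primary outcome, so a poor ESI would be exposed there. This is partly right. But accuracy is judged against the resection and so only in operated patients, expected to be 0.50 × 250 = 125. It also does not change what the utility percentage means.

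Two stronger readings are tempting and are not supported:

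- A reader might infer that an inaccurate ESI will score higher. The model gives only that it can. It assumes that every disagreement is acted on, whereas code 2 provides for discordance without change, and ESI is weighed with all other data.
- A reader might count the 46 regions and infer that a randomly placed source would almost always disagree and so inflate the outcome. The reports contain up to six spike clusters, onset and peak images, interictal and ictal analyses, several methods and an error ellipsoid, and an implantation plan may cover several sites. The documents do not fix the chance of overlap, and disagreement is not the same as change.

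It is also fair to object to counting only codes 3, 5 and 6 as possible utility. Lack of a criterion for codes 4, 7 and 8 does not show lack of benefit, and treating them as failures would bias the useful share downward.

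**Conclusion.** The point holds in a limited form. The stated outcome is the percentage of patients with any ESI-triggered change. It does not use the one-year rating, gives no credit to correct confirmation, and cannot by itself support a conclusion that ESI is clinically useful. That much follows from the text without any model.

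That the percentage can be higher for a less accurate ESI is shown by the model (73.1% at accuracy 0.4 against 40.5% at 0.9 with t = 0.66 and K = 46). It rests on assumed team accuracy, independent errors and action on every disagreement. The size of the gap between changed and usefully changed cannot be derived from the documents; the 9% to 21% against 30% above is illustrative.

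The percentage changed remains a legitimate descriptive measure. The Appendix-4 rating also has limits: it has no counterfactual, since a patient rated a success might have done as well without the change. It does, however, withhold credit from rated changes that failed.

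**What to change.** 1. Keep the percentage changed and label it change in management.
2. Add to the clinical-utility outcome the percentage of patients whose change was rated useful at one year under the existing Appendix-4 criteria. The denominator is all patients with both decision steps.
3. Beside it, on the same denominator, show the percentages rated not useful and unrated. The unrated category holds changes without an Appendix-4 criterion (codes 4, 7 and 8) and changes that were not carried out. Count these neither as useful nor as failures.
4. State that any conclusion that ESI is clinically useful rests on the useful share, read together with the other two.

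The cost is protocol wording and one extra table from data already planned; no clinical rule changes. The headline figure will be smaller and available only after the one-year assessment.

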Four centers (Copenhagen, Dianalund, Freiburg and Prague) will do “manual” ESI, as part of the preoperative workup. In this sub-group, the performance of the various pipelines and analysis methods will be compared. The MDTs in these centers will first get access to the “manual” ESI, after scoring the clinical utility for the automated analysis.

*Authorship:*

Principal investigator, guarantor and corresponding author: [name].

Co-authors:

- Epilog team: [name], [name], [name], [name]
- BESA-team: [name], [name], [name], [name]
- From the participating centers: one author per center - provided the center submitted complete datasets for more than 10 patients, including at least 5 operated patients; two authors per center - provided the center submitted complete datasets for more than 20 patients, including 10 operated patients.

**The study protocol will be registered and published at the start of the study. As the goal of the study is to assess the accuracy and clinical utility of ESI methods and not compare products of companies, the results will not be presented as a comparison between companies/products, but as comparison between different analysis methods and strategies.**

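### In the four manual-ESI centres no decision is logged after manual ESI is released, so the one-year usefulness rating can credit or fault automated ESI for a plan it did not determine

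*Protocol*

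**What the plan says.** Three parts of the protocol bear on this.

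- **Paragraph on the four manual-ESI centres (before Authorship).** These centres perform manual "ESI, as part of the preoperative workup". Their teams see the manual "ESI, after scoring the clinical utility for the automated analysis".
- **Appendix-4, decision log.** "The multidisciplinary teams take decisions in two steps": step I is "Considering all data, except ESI" and step II is "Adding ESI to all other data". Given the release order, ESI at step II in these four centres can only be the automated analysis. The change between the steps is coded, and there is no later step.
- **Outcome definitions.** Under Reference standard, clinical utility is "the percentage of patients in whom ESI changed decision on patient management". Appendix-4 adds a second assessment: "At one-year follow-up, the changes are categorized as useful or not useful". Rule (a) reads "change from stop to ICR: the ICR localized the source". Rule (b) asks whether the electrodes placed because of source imaging found the source. Rule (c) asks whether a patient moved from implantation to operation became free of seizures.

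**The concern.** Manual ESI in these centres is clinical information that arrives after the last logged decision and, being part of the presurgical workup, before any operation. It can confirm, alter or reverse the step II plan. The usefulness rating does not judge the plan as recorded at step II. It looks at the result of the recording or operation that was carried out. If manual ESI changed that plan, the result belongs to a decision that Appendix-4 does not capture, and the rating can go either way for automated ESI without good reason.

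At stake is the meaning of the usefulness figure. It is the only part of the clinical-utility assessment that asks whether the changes prompted by automated ESI did any good. The gap is one of data capture: an SAP, which is not at hand, could not reliably recover a decision that was never recorded.

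**Working it through.** The protocol states no figure on this point, so there is none to reproduce. The check follows the order of events, then applies each usefulness rule to a plan that manual ESI revised.

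**Order of events in the four centres**

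1. Step I: decision without ESI, logged.
2. Step II: decision with automated ESI, logged; change coded.
3. Manual ESI released to the team.
4. Any revised decision: not logged in Appendix-4.
5. Implantation, operation or neither.
6. One-year rating of the change between items 1 and 2, using the result of item 5.

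**Changed-decision percentage.** It depends on items 1 and 2 only, and both precede item 3. Nothing manual ESI does later can enter it.

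**Usefulness rules under a revision at item 4**

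| Rule | Plan altered by manual ESI | Plan reversed by manual ESI |
|---|---|---|
| (a) stop to intracranial recording | Sites moved or added on manual ESI; the recording localises; rule met | No recording takes place; rule cannot be met, and nothing says whether the change is then not useful or unrated |
| (b) additional implantation sites | Rule refers to source imaging in general, so an electrode placed on manual ESI can satisfy it | Sites not implanted; rule cannot be met; same silence |
| (c) implantation to operation | Resection site changed on manual ESI; seizure freedom credited | Patient goes back to implantation, is operated later and becomes seizure-free; rule met although the step II change was not carried out |

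False credit is therefore possible under all three rules when the plan is altered, and under (c) also when it is reversed. Reversals under (a) and (b) give no false credit, but may be rated as failures of a change that was never tested.

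**Whether other recorded items fill the gap.** Appendix-2 records whether a resection was done and where, so a cancelled or relocated operation would be visible, but not its cause. The method-attribution list in Appendix-4 covers SLORETA, ECD and CLARA and has no entry for manual ESI. The implantation actually carried out is not among the items listed in the document.

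**Scale (illustration only).** Exposed share of all logged changes = (share of changes arising in the four centres) × (probability that the plan is revised after manual ESI). Both inputs are assumed.

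| Share in four centres | Revision 0% | Revision 5% | Revision 30% |
|---|---|---|---|
| 20% | 0 | 0.20 × 0.05 = 1% | 0.20 × 0.30 = 6% |
| 40% | 0 | 0.40 × 0.05 = 2% | 0.40 × 0.30 = 12% |
| 60% | 0 | 0.60 × 0.05 = 3% | 0.60 × 0.30 = 18% |

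In patients: if 20% of the planned 250 have a changed decision (assumed), there are 250 × 0.20 = 50 changes. The exposed number is then 50 × 0.01 = 0.5 to 50 × 0.18 = 9. These are ratings that could be affected, not ratings shown to be wrong.

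**The case against.** The best reply is that the release order is a strength. Holding manual ESI back until automated ESI has been scored keeps the measured change free of it. That stands in full. A reader might infer from the missing third step that the changes themselves are wrongly attributed to automated ESI. The documents do not support this: the outcome is a change in the recorded decision, a later reversal does not undo it, and a change first prompted by manual ESI cannot appear between steps I and II. For the same reason, the exposed numbers should not be set against the sampling error of the changed-decision percentage, which is a different quantity.

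A second reply is that the rules screen out reversed plans. This holds for (a) and (b) as regards false credit. It does not hold for (c), nor for plans that were altered but not cancelled.

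A third is that the four centres may not be special. The protocol nowhere says that step II decisions are carried out elsewhere, nor how these centres are combined with the rest. Both are fair, so a contrast between executed decisions elsewhere and provisional ones here cannot be asserted. What sets the four centres apart is a planned release of further source imaging after the last logged step.

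Finally, the CRFs are not shown and may record the final plan. That could reduce the gap, but Appendix-4 as written fixes two steps and gives no rule for an executed plan that departs from step II.

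**Conclusion.** The point holds for the one-year usefulness rating in the four manual-ESI centres, and only there. The rating can credit or fault automated ESI for a plan that manual ESI altered or reversed; the documents do not show that it will. The changed-decision percentage, which is how the protocol defines clinical utility, stands as planned.

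The size is unknown. Under the assumed ranges above it runs from 1% to 18% of logged changes, and it is zero if no plan is revised after manual ESI. Clinical utility is a secondary outcome and the usefulness rating appears only in Appendix-4, so the consequence is limited. The correction is still worth making before data collection, because it cannot be made reliably afterwards. The conclusion rests on the two-step log being complete as printed and on the CRFs not already holding the decision taken after manual ESI.

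**What to change.** 1. In the four centres, add a step III line ('adding manual ESI') to Appendix-4 with the existing decision and change codes. The codes already cover implantation to stop and operation to implantation; other revisions fit under Other.
2. State in the usefulness definition that a step I to II change is credited to automated ESI only if the executed plan matches step II.
3. Report changes altered or reversed at step III as a separate category, with their number. Do not drop them: keeping only changes that manual ESI left standing could select for success and inflate the apparent usefulness of automated ESI.
4. Show the usefulness result with and without these four centres.

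The cost is one form line in four centres and one analysis line. The drawback is that fewer changes will be rated as useful or not useful. The fix concerns only what is recorded and how it is rated, and leaves patient care as it is.

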*Additional data provided by the participating centers:* demographic and clinical data (appendix-2), results of the neuroimaging (MRI, PET, SPECT) localization at sub-lobar level (appendix-3), and screen-shots (axial, coronal and sagittal planes) and changes in patient management (appendix-4). These data will not be available for those running the automated source imaging. After the operation: information on the resection, the pathology, postoperative MRI, outcome one year after the operation.

*Automated source imaging:* Epilog and BESA will run the automated source imaging – both for interictal epileptiform discharges (EDs) and ictal signals. A report summarizing the results will be send to the corresponding center and the PI in a one-step procedure.

The automated source imaging consists of 2 phases:

1. Automated detection of EDs
2. Source imaging of each spike cluster and seizure onset epoch.

The complete procedure will be done using automated algorithms without subjective interactions during spike detection and source imaging. For each detected spike cluster and seizure-onset, source imaging will be done at two different time-epochs: at onset and at peak. The two analysis-teams will use two different methods for defining the onset epoch. The time-points (or epochs) for onset and peak will be specified for each spike cluster using the peak channel in the common average montage.

The analysis-teams will provide source images in axial, coronal and sagittal planes. Epilog will use SLORETA for interictal analysis and LORETA followed by functional connectivity analysis for ictal source imaging. BESA will use Multiple Dipole Analysis, Volume- and Cortical-CLARA.

Individual head models will be used for the analyses. BESA will use FEM or an approximate model if the quality of an MRI should be insufficient. Epilog will use a head model with six different tissue classes (scalp, skull, cerebrospinal fluid, gray matter, white matter and air). The finite difference method is used to calculate the lead-fields, which describe the relation between current source in the brain and measured potentials at the electrodes.

Each analysis-team will send a report to the center that submitted the data and to the PI. The report will contain the following:

- Patient code and descriptive data about the recording (duration, number of electrodes)
- Data of up to six clusters in the order of the number of spikes in each cluster

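### Cross-team contrasts of automated ESI are aliased with each team's pipeline, so they cannot support conclusions about the inverse method

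*Protocol*

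**What the plan says.** The protocol paragraph on automated source imaging gives each automated inverse method to a single team. For one team, "Epilog will use SLORETA for interictal analysis and LORETA followed by functional connectivity analysis for ictal source imaging"; for the other, "BESA will use Multiple Dipole Analysis, Volume- and Cortical-CLARA".

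The same paragraph separates the teams in two further respects:

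- Onset rule: "The two analysis-teams will use two different methods for defining the onset epoch".
- Head model: "BESA will use FEM or an approximate model if the quality of an MRI should be insufficient", whereas Epilog uses a six-tissue model with finite-difference lead-fields.

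It makes automated detection of discharges the first phase of the imaging that both teams run. Each team's report lists its own clusters and spike counts. One of the two definitions of the dominant cluster depends on those counts: "Quantitative definition: the cluster with the highest number of spikes". The other relies on a spike marked by the center.

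On interpretation, the opening summary names as a secondary outcome "inter-ESI-methods agreement (at sub-lobar level". The statement that closes the Authorship section says that "the results will not be presented as a comparison between companies/products, but as comparison between different analysis methods and strategies".

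**The concern.** A reader who sees SLORETA compared with CLARA, under a statement that companies are not being compared, will take the result as a property of the two inverse solutions. The design does not isolate that. Changing from SLORETA to CLARA also changes the team, the head model and, for onset images, the rule that selects the imaged epoch. It probably changes which spikes were detected and how they were clustered as well.

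Two conclusions are at stake. A cross-team difference in sensitivity or specificity could be credited to an algorithm when another step produced it. Cross-team disagreement at sub-lobar level could be read as disagreement between source-imaging methods when the teams had imaged different discharges or different epochs. A supplementary method choice in later practice could then rest on the wrong component.

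**Working it through.** The protocol gives no figure on this point, so there is none to reproduce. The check maps methods to pipelines, counts the affected pairs and then illustrates a possible size.

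**1. What changes across teams**

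| Component | Epilog | BESA | Basis |
|---|---|---|---|
| Interictal inverse method | SLORETA | dipoles, Volume-CLARA, Cortical-CLARA | stated |
| Ictal inverse method | LORETA plus connectivity | dipoles, CLARA | stated (BESA's ictal use appears in Appendix-4) |
| Head model | six-tissue, finite difference | FEM, or approximate if the MRI is poor | stated |
| Onset rule | own | own | stated to differ |
| Spike detection, clustering | own | own | inferred from both teams running detection and reporting clusters |

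No step runs one team's inverse method on the other team's clusters, onset epoch or head model.

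**2. What is shared.** Both teams receive the same uploaded EEG and MRI. The fiducials are cross-checked, the ictal epochs are suggested by the centers, and the 20-spike minimum and the error ellipsoid (2.5 cm radial, 1.8 cm tangential) are common. Time-points follow one stated convention: they "will be specified for each spike cluster using the peak channel in the common average montage". With the onset rules stated to differ, peak is the better matched of the two time-points.

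**3. Pairs affected.** There are 1 + 3 = 4 automated interictal methods.

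- All pairs: 4 × 3 / 2 = 6.
- Cross-team pairs: 1 × 3 = 3. All are aliased with head model and, at onset, with onset rule.
- Within-BESA pairs: 3 × 2 / 2 = 3. None is aliased with team, because head model and onset rule are set per team.

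Onset versus peak and interictal versus ictal can also be contrasted within a team.

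**4. Illustration of size (all rates assumed).** Let q be the proportion of patients in whom the two teams' largest clusters are the same discharge, a = 75% the agreement on the same discharge, and f the agreement on different discharges.

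Observed agreement = q·a + (1 − q)·f, so the loss relative to a is (1 − q)(a − f).

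| q | f = 10%: agreement (loss) | f = 40%: agreement (loss) |
|---|---|---|
| 95% | 71.75% (3.25) | 73.25% (1.75) |
| 80% | 62.0% (13.0) | 68.0% (7.0) |
| 70% | 55.5% (19.5) | 64.5% (10.5) |

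For example, at q = 70% and f = 10% the loss is 0.30 × 0.65 = 0.195. The f = 40% column allows for two clusters in one patient lying in the same sub-lobar region. The illustration concerns the quantitative dominant cluster only. It does not apply to ictal images and bears only weakly on the center-marked cluster.

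**The case against.** The strongest reply is that the protocol already allows the right reading. The closing statement speaks of strategies as well as methods, and the paragraph on manual ESI speaks of comparing pipelines. A complete pipeline is a strategy, and agreement between pipelines is a legitimate descriptive outcome that makes no claim about cause. This stands, and it makes the remedy a clarification. It does not remove the need for one, because the same statement also permits the reading that the design cannot support.

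A second reply is that much has been harmonised: inputs, fiducials, ictal epochs, the ellipsoid and a center-marked dominant spike. This also stands, and it narrows the different-discharge argument mainly to the quantitative definition. It leaves the head model aliased everywhere and the onset rule aliased at onset.

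Two stronger inferences are tempting and should be resisted.

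- A reader might conclude that every ESI method is tied to one company and that no method comparison is possible. The documents do not support this: three automated interictal pairs lie within one team, and four centers perform manual ESI. Manual ESI does not break the alias between the automated methods, however, since it is a further workflow and not a crossing of them.
- A reader might take separate spike detection as stated fact. It is a reasonable inference, but no sentence says that the detectors or clustering rules differ.

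Finally, redefining the agreement outcome on matched clusters would condition on both teams having found the same discharge. That could overstate the agreement of automated ESI, of which detection is a part.

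**Conclusion.** The point holds for cross-team contrasts of automated ESI. Any difference or disagreement between SLORETA/LORETA and dipole/CLARA is also one between head models and, at onset, between onset rules; both are stated. It is probably also one between detection and clustering steps, which is inferred. It cannot be attributed to the inverse method.

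The scope is limited. Three of the six automated interictal pairs are affected. The within-BESA pairs, the within-team strategy contrasts, the primary accuracy of each pipeline and the overall percentage of changed decisions are not. Cross-team agreement remains estimable as agreement between pipelines; only its cause is confounded.

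The size is unknown. On the assumed rates, discharge mismatch alone would lower observed agreement by about 3–20 points if different discharges agree in 10% of patients, and by about 2–11 points if they agree in 40%. These ranges illustrate and do not predict.

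**What to change.** 1. Amend the closing statement of the Authorship section. Cross-team accuracy contrasts and cross-team agreement are reported as comparisons of complete pipelines (detection, onset rule, head model and inverse method). Conclusions about the inverse method are limited to within-team pairs: dipole, Volume-CLARA and Cortical-CLARA.
2. Keep whole-pipeline agreement as the secondary outcome.
3. Add two supplementary analyses: agreement on the center-marked (qualitative) cluster at peak, and how often the two teams' largest clusters are the same discharge. The averaged waveforms and voltage maps required in both reports allow the matching.

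The cost is wording plus the work of matching clusters; no new patients or recordings are needed. The cross-team claims become narrower. The supplementary agreement analysis loses patients without a matching cluster and does not equalise the head models, so the relabelling in item 1 is the essential change.
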